Women of childbearing potential must agree to use an adequate method of contraception during the study until 30 days after the last treatment. Males must be surgically or biologically sterile or agree to use an adequate method of contraception during the study until 30 days after the last treatment.

3.2.2 Exclusion Criteria:

- I) New York Heart Association class III or IV heart disease, active ischemia or any other uncontrolled cardiac condition such as active angina pectoris, clinically significant cardiac arrhythmia that requires therapy in the opinion of the treating physician or PI, uncontrolled hypertension (blood pressure > 160 systolic and > 110 diastolic not responsive to antihypertensive medication), uncontrolled diabetes mellitus in the opinion of the treating physician or PI, or uncontrolled congestive heart failure in the opinion of the treating physician or PI.
- 2) Myocardial infarction in the previous 12 weeks (from the start of treatment).
- 3) Active and uncontrolled disease/infection as judged by the treating physician.
- 4) Pregnant or breastfeeding
- 5) Known Human Immunodeficiency Virus seropositivity
- 6) Any other medical, psychological, or social condition that may interfere with study participation or compliance, or compromise patient safety in the opinion of the investigator or medical monitor
- 7) Acute promyelocytic leukemia (APL).

4.1 TREATMENT PLAN:

4.2 Treatment Plan in Phase I and II:

In Phase I six patients will be treated with vosaroxin administered intravenously on days 1 and 4 at a dose of 90 mg/m² for a total dose of 180 mg/m²/cycle in combination with decitabine at a dose of 20 mg/m² intravenously on days 1 through 5. Patients will be assessed for non-hematological toxicities during the first 28 days on therapy and for hematological toxicities for the first 42 days on therapy. The purpose of the lead-in Phase I portion is to ensure safety. If first cycle DLT is observed in 1 or less of 6 patients treated this dose level will be the MTD and the study will transit to the Phase II portion. A summary and rationale for continuation of treatment

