The purpose of the lead-in Phase I portion is to ensure safety. If first cycle DLT is observed in 1 or less of 6 evaluable patients treated, this dose level will be considered the MTD and the study will transit to the Phase II portion. If first cycle DLT is observed in 2 or more of 6 evaluable patients treated, 6 additional patients will be treated on the Phase I portion at a lower dose level as detailed below until we define a Phase II dose schedule (MTD) at which 1 or less out of 6 patients on the Phase I experience first cycle DLT. After the Phase I portion ensures safety thereby defining the Phase II dose schedule, all subsequent patients will receive the same dose schedule in the Phase II portion.

a. The first 6 patients on study (Phase I portion of study) will receive vosaroxin IV on days 1 and 4 at a dose of 90 mg/m^2 in the first cycle (induction 1) for a total dose of $180 \text{ mg/m}^2/\text{cycle}$ in combination with decitabine at a dose of 20 mg/m^2 intravenously for 5 consecutive days (Days 1 to 5). If DLT's are observed in 0-1/6 in phase I, this dose level will be considered to be the MTD for this study and the study will open broadly for the Phase II at this dose schedule.

b. If DLT's are observed in 2/6 or more patients, this dose level would exceed the MTD, and the induction chemotherapy dose will be reduced to vosaroxin at a dose of 70 mg/m^2 IV on days 1 and 4 in the first cycle (induction I) for a total dose of $140 \text{ mg/m}^2/\text{cycle}$ in combination with decitabine at a dose of 20 mg/m^2 intravenously for 5 consecutive days (Days 1 to 5). Six patients will be treated to evaluate the safety of this schedule, and after consultation with and approval of the PI. If DLTs are observed in 0-1/6 in phase I, the study will open broadly for the phase II at this schedule at this dose schedule.

c. If DLT's are observed in 2/6 or more patients, this dose level would exceed the MTD, and the induction chemotherapy dose will be reduced to vosaroxin at a dose of 50 mg/m^2 IV on days 1 and 4 in the first cycle (induction 1) for a total dose of $100 \text{ mg/m}^2/\text{cycle}$ in combination with

decitabine at a dose of 20 mg/m² intravenously for 5 consecutive days (Days 1 to 5). Six patients will be treated to evaluate the safety of this schedule, and after consultation with and approval of the PI. If DLTs are observed in 0-1/6 in phase I, the study will open broadly for the phase II at this schedule at this dose schedule.

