10.1 STATISTICS

10.2 Sample size

This will be a single arm, single center, open label study of the combination of vosaroxin with decitabine as an induction therapy in previously untreated patients with acute myeloid leukemia (AML) or high risk myelodysplastic syndrome (MDS) who are elderly (age \geq 60) and/or unable to tolerate standard therapy. A total of up to 84 patients will be enrolled in the study.

Phase I

A total of up to 24 patients will be accrued into the Phase I part.

Phase II

A total of up to 60 patients (including 6 patients treated at the MTD from the Phase I part) will be recruited for the Phase II part.

The primary efficacy endpoint is overall response rate (ORR). $ORR = CR + CR_p + CR_i$. Responses will be evaluated at the end of the first induction cycle and second induction cycle (if a second induction cycle is needed). With a null hypothesis of 40% historical response rate, a sample size of 60 patients would be required to demonstrate a response rate of 60% for the combination of vosaroxin and decitabine using a one-sample exact binomial test and with a two-sided alpha of 0.05 and a power of 82%.

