10.3 Statistical Design

Phase I

. In phase I portion of the study the MTD is defined as the highest daily oral dose evaluated at which $<33\%$ of patients experience a DLT. Six patients will be treated. If clinically significant drug related Grade 3-4 toxicity is observed during the first cycle in 0-1 patient out of 6 patients, this will define a safe schedule and the study will open broadly for the Phase II portion. If drug related Grade 3-4 toxicity is observed in 2 or more of 6 patients, this dose will exceed DLT, and a lower dose schedule will be investigated in an additional 6 patients. Please refer to Section 4.4. The dosing algorithm is presented in Table?.

Table 7. Dosing algorithm

Dose Level	Vosaroxin D1&D4	Decitabine
-3	50mg/mL	20 mg/m ² (Days 1-4)
-2	50 mg/m ²	20 mg/m ² (Days 1-5)
-1	70 mg/m ²	20 mg/m ² (Days 1-5)
0	90mg/m ²	20 mg/m ² (Days 1-5)

Phase II

Efficacy

The historical data suggested an ORR of 40% and with the assumption that the improved ORR is 60% the study will be stopped early if the observed patients' data suggest that:

$$\Pr(n > 0.6J \text{ data}) < 0.025$$

Here n is the overall response rate (ORR). That is, if at any time during the study we determine that there is a less than 2.5% chance that the average ORR is greater than 60%, we will terminate the study. The ORR is assumed to follow a non-informative prior of Beta (1.2, 0.8). The stopping boundaries for ORR, based on these assumptions and monitoring conditions are found in table 8. We will apply these stopping boundaries starting from the fifth patient and in cohorts of 5. For example, accrual will cease if only 2 or less than 2 patients experience overall response among the first 10 patients treated. The operating characteristics are summarized in table 8.

Table 8. Stopping boundaries for ORR

Number of patients evaluated	5	10	15	20	25	30	35	40	45	50	55	60
------------------------------	---	----	----	----	----	----	----	----	----	----	----	----

for response												
Number of patients with response (i.e., CR, CRp or CRi)	0	0-2	3-5	6-7	8-9	10-12	13-15	13-17	18-20	21-22	23-25	26-28

Table 9. Operating characteristics for monitoring of overall response rate

True overall Response Rate	Early Stopping Probability		Sample size		
			25%, 50%, 75%		
0.35	0.974		10	15	30
0.40	0.888		15	20	35
0.45	0.702		15	35	60
0.50	0.442		30	60	60
0.55	0.209		60	60	60
0.60	0.079		60	60	60
0.65	0.027		60	60	60

Toxicity Monitoring

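### Phase I does not close a dose level to accrual at the second DLT, so up to four more patients per level could be treated after the go/no-go decision is already fixed (minor, cheap to mend)

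*Combined protocol and SAP*

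**What the plan says.** Every statement of the Phase I rule is framed on six patients.

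- **Section 4.2:** "In Phase I six patients will be treated with vosaroxin administered intravenously". Section 3.2 has the same structure.
- **Section 4.4, acceptance:** "If first cycle DLT is observed in 1 or less of 6 evaluable patients treated, this dose level will be considered the MTD".
- **Section 4.4, rejection:** "If first cycle DLT is observed in 2 or more of 6 evaluable patients treated, 6 additional patients will be treated" at a lower level. The step-by-step list adds: "If DLT's are observed in 2/6 or more patients, this dose level would exceed the MTD".
- **Section 4.4, each lower level:** "Six patients will be treated to evaluate the safety of this schedule, and after consultation with and approval of the PI".
- **Section 10.3, Phase I:** "Six patients will be treated", followed by the same split between 0-1 and 2 or more.
- **Section 10.2:** "A total of up to 24 patients will be accrued into the Phase I part". Table 7 lists four dose levels.

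Four other provisions bear on the point.

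- Section 7.2 (Study Stopping Rules) lets the principal investigator and the IND Office suspend enrolment or terminate the study. The first reason it lists is the incidence or severity of treatment-related reactions. It gives no count or rate.
- Section 9.3 sends all SAEs to the IND Office within five working days. Unexpected, related, life-threatening or fatal events go by the next working day.
- The toxicity boundary in 10.3 (Tables 10 and 11) is stated for Phase II.
- The IND Office cohort summaries in 4.2 and 4.4 come when a level is left or when six patients have been treated at the selected MTD. They are not looks within a cohort.

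**The concern.** A count of DLTs can only rise. Once two of the patients at a level have had a DLT, the final tally cannot be 0 or 1 of 6, so the move down is certain whatever happens to the rest. The text says nothing about accrual at that moment. Read literally, a level with DLTs in its first two patients would still take four more.

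What is at stake is avoidable exposure at a level that the plan's own rule has already rejected. By section 2.2.3 this is the first clinical use of the combination, and by Table 7 it starts at the highest of the four levels. Section 4.4 gives ensuring safety as the purpose of this portion. Phase II has a numerical toxicity check every five patients; Phase I has none within the cohort.

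**Working it through.** **Inputs.** Cohort size 6 and threshold 2 (4.4, 10.3); four levels (Table 7); Phase I maximum 24 (10.2); DLT windows of 28 days (non-hematologic) and 42 days (hematologic) (4.4). The documents give no true DLT rate, so p is an assumption, shown over 10% to 60%.

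**1. The plan's own figures.** 4 levels × 6 patients = 24, which reproduces the stated maximum and supports reading the rule as full cohorts. The threshold also agrees with the MTD definition in 10.3 (below 33%): 1/6 = 16.7% is below it, and 2/6 = 33.3% is not.

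**2. When the outcome is fixed.** Let T be the patient at whom the second DLT falls. Then

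P(T = k) = (k − 1) p² (1 − p)^(k − 2), for k = 2 to 6.

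Patients treated after the decision is fixed number 6 − T, so at most 4. This step assumes each outcome is known before the next patient starts.

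At p = 0.40:

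| k | P(T = k) | 6 − k |
|---|---|---|
| 2 | 0.1600 | 4 |
| 3 | 0.1920 | 3 |
| 4 | 0.1728 | 2 |
| 5 | 0.1382 | 1 |
| 6 | 0.1037 | 0 |

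The probabilities sum to 0.767, the chance that the level fails. Mean patients after the second DLT = 4(0.1600) + 3(0.1920) + 2(0.1728) + 1(0.1382) = 1.70. Given that the level fails, this is 1.70 / 0.767 = 2.22.

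**3. Across assumed rates.**

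| True DLT rate | P(level fails) | P(second DLT before patient 6) | Mean spared per level | Mean spared if level fails |
|---|---|---|---|---|
| 10% | 0.114 | 0.081 | 0.17 | 1.50 |
| 20% | 0.345 | 0.263 | 0.59 | 1.70 |
| 30% | 0.580 | 0.472 | 1.13 | 1.94 |
| 40% | 0.767 | 0.663 | 1.70 | 2.22 |
| 50% | 0.891 | 0.812 | 2.25 | 2.53 |
| 60% | 0.959 | 0.913 | 2.74 | 2.86 |

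Expected DLTs among the spared patients are p times the mean spared: about 0.34, 0.68 and 1.1 per level at 30%, 40% and 50%.

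**4. Effect on the decision.** With all six treated, P(fail) = 1 − (1 − p)^6 − 6p(1 − p)^5. At p = 0.40 this is 1 − 0.0467 − 0.1866 = 0.767, the same as the sum in step 2. Closing at the second DLT leaves acceptance and rejection unchanged at every p.

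**5. Effect of timing.** If m patients have already started when the second DLT is recognised, the saving is 6 − m. The plan sets no stagger, so m can be 6 and the saving zero. It cannot be negative. Step 3 therefore gives upper limits.

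**6. What later patients still tell.** Borrowing the Phase II toxicity prior, Beta(0.6, 1.4), purely for illustration, the probability that the DLT rate exceeds 33% is 0.91 after 2/2, 0.45 after 2/6 and 0.745 after 3/6. The decision is fixed, but the estimate of the rate is not.

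**The case against.** The strongest reply is that the plan does not order anyone to keep enrolling, and that oversight exists. Both statements are correct. A reader might infer that six must be treated even after two DLTs. Full cohorts are the natural reading, but no sentence requires accrual to continue. A reader might also infer that nothing could stop accrual. In fact 7.2 expressly allows enrolment to be suspended, and SAE reports under 9.3 reach the IND Office before any cohort summary. What is missing is a stated trigger. The Phase II boundary does not supply one: besides its scope, its first entry in Table 10 is 4 of 5 patients, well above the Phase I threshold.

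Three further inferences fail.

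- **That the later patients are treated at a dose known to be too toxic.** Exceeding the MTD is the rule's label. A level with a true DLT rate of 1/6 still shows 2 or more of 6 with probability 0.26.
- **That they yield no information.** Step 6 of the working shows otherwise; only the go/no-go outcome is unaffected.
- **That they take places from lower levels.** The maximum of 24 already provides four full cohorts.

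The point may also come late for the top level. Section 4.5 refers to experience to date when asking to lower the Phase II induction dose of vosaroxin from 90 to 70 mg/m², which suggests that the 90 mg/m² level had been used by then. The documents do not say that Phase I is complete, and its rule remains in the current text.

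**Conclusion.** The point holds as a gap in the Phase I rule, of minor weight. The second DLT settles the outcome at a level, and no Phase I text says what happens to accrual then. Up to four patients per level could be treated afterwards with no effect on the decision. The average that could be spared is at most about 1.1, 1.7 and 2.25 per level at true DLT rates of 30%, 40% and 50%, or 1.9, 2.2 and 2.5 if the level fails.

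These sizes rest on assumed DLT rates, independent patients, and outcomes known one at a time. With fast entry the real saving could be close to nil. The documents support possible exposure after the decision is fixed. They do not show that such exposure is prescribed or certain.

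**What to change.** For any Phase I level still to be run, add to 4.4 and 10.3, and align 3.2 and 4.2 with it:

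> A dose level closes to new patients as soon as two patients at that level have had a DLT. The level is then declared to exceed the MTD, and the cohort summary goes to the IND Office without waiting for six patients. Acceptance still requires 0-1 DLT among 6 evaluable patients.

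This uses the protocol's existing threshold, sets no dose, and concerns new entry only. It adds no patients, visits or tests, and leaves the error rates as they are. The price is less descriptive safety and response data at a rejected level. Because the sentence adds no staggering, the benefit depends on the pace of enrolment, and the sponsor should state that pace or its handling alongside. If Phase I is already complete, a line saying so would dispose of the point.

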d. If DLT's are observed in 2/6 or more patients, this dose level would exceed the MTD, and the induction chemotherapy dose will be reduced to vosaroxin at a dose of 50 mg/m² IV on days 1 and 4 in the first cycle (induction 1) for a total dose of 100 mg/m²/cycle and the decitabine will be reduced to 20 mg/m² IV for only 4 consecutive days (Days 1 to 4). Six patients will be treated to evaluate the safety of this schedule, and after consultation with and approval of the PI. If DLTs are observed in 0-1/6 in phase I, the study will open broadly for the phase II at this schedule at this dose schedule.

After the first 6 subjects have been treated with vosaroxin and decitabine at the selected MTD (either dose-level a, b, or d), and assessed for toxicity, a summary and rationale to continue enrollment will be provided by the study team to the IND Office including a separate cohort summary for each dose level tested. These will be reviewed by the IND Office Medical Monitor. The IND Office Medical Monitor will indicate whether the study may continue enrollment.

4.5 Induction Therapy in Phase II:

Following the phase I portion to ensure safety, all subsequent patients will receive the following induction regimen (induction 1):

- a. Vosaroxin intravenously on days 1 and 4 at a dose of 70 mg/m² for a total dose of 140 mg/m²/cycle (days 1 and 4), or the final induction dose (MTD) determined in phase I.
- b. Decitabine IV at a dose of 20 mg/m² for 5 consecutive days (days 1 to 5), or the final induction dose (MTD) determined in phase I.

The 70mg/m² day 1 and 4 dosage of vosaroxin has been implemented in the REVEAL-I study (single agent vosaroxin in elderly AML) and was felt to be as efficacious as the 90 mg/m² dose with a lower incidence of mucositis. Based on our current experience and the data from REVEAL 1 we would like to request IND approval to reduce the vosaroxin induction dose from 90 mg/m² days 1 and 4 to 70 mg/m² days 1 and 4 with the intention of decreasing toxicity while maintaining equivalent efficacy.

Treatment may be repeated every 4-7 weeks. If a dose is missed, the patient may take the missed dose if it has been less than 48 hours.

Patients, who have not achieved any response (CR, CRp, Cri) following the initial induction (induction 1) course, can receive one additional induction course (induction 2) at the same dose as induction 1 or other dose modifications for re-induction may be made in the best interest

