of patient after discussion with the PI to optimize response if indicated. The re-induction must be given within 4-8 weeks of documented refractory leukemia. Re-induction (Induction 2) may be given beyond the stipulated 8 weeks if approved by the study PI.

If the bone marrow aspirate and/or biopsy(s) performed after the induction courses reveal a remission marrow (CR/CRp/CRi), then the patient may proceed to consolidation therapy at the discretion of the treating investigator. In addition, any clinically significant drug-related, nonhematologic toxicity experienced by a patient should return to < grade 2 or the baseline grade before the patient continues treatment.

Should the patient not achieve CR/CRp/CRi after the second induction course, they will be taken off study unless clinical benefit is observed and the PI approves continuation of therapy on the protocol.

Hydroxyurea 1.5 g orally daily for up to 10 days is allowed in the first induction course for white blood count $>30.0 \times 10^9/L$.

4.6 Post-remission Therapy in Phase I and Phase II:

Patients achieving a CR/CRp/CRi may receive consolidation/ maintenance therapy as follows:

Consolidation - Up to 5 additional cycles as follows:

- a. Vosaroxin intravenously on days 1 and 4 at a dose of 70 mg/m^2 for a total dose of $140 \text{ mg/m}^2/\text{cycle}$ (days 1 and 4). Decitabine at a dose of 20 mg/m^2 intravenously for 5 consecutive days (days 1-5), or the final induction dose determined in phase I.

Patients who achieve a CR/CRp/CRi should receive the consolidation cycle no sooner than 28 days from Day 1 of the previous induction or re-induction cycle provided their peripheral blood counts have recovered (ANC $\geq 1.0 \times 10^9/L$ and platelet count $\geq 50 \times 10^9/L$). If patient has documented CRp they may proceed with consolidation cycles even if the platelet count remains $\leq 50 \times 10^9/L$ if approved by the PI. If patient has documented CRi they may proceed with consolidation cycles even if the platelet count remains $\leq 50 \times 10^9/L$ and/or ANC $\leq 1.0 \times 10^9/L$ if approved by the PI.

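### Sections 3.2 and 4.4 set the Phase II vosaroxin dose at the Phase I MTD, but 4.5 gives 70 mg/m² 'or' the MTD with no rule for choosing, so two induction doses could be pooled

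*Combined protocol and SAP*

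**What the plan says.** **Dose from the Phase I rule.** Section 4.4 makes a level the MTD when 0 or 1 of six patients has a first-cycle DLT. The first level is 90 mg/m² on days 1 and 4. Item (a) says that if this level passes, "the study will open broadly for the Phase II at this dose schedule". Sections 3.2 and 4.4 both add that "all subsequent patients will receive the same dose schedule in the Phase II portion".

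**Dose in the Phase II section.** Section 4.5 gives vosaroxin at "70 mg/m² for a total dose of 140 mg/m²/cycle (days 1 and 4), or the final induction dose (MTD) determined in phase I". It frames the move to 70 as a request: "we would like to request IND approval". What the authors ask for is leave to "reduce the vosaroxin induction dose from 90 mg/m² days 1 and 4 to 70 mg/m² days 1 and 4". They describe the aim of this change as follows: "with the intention of decreasing toxicity while maintaining equivalent efficacy". The reasons given are experience so far and a single-agent study in elderly AML, not two or more DLTs in six.

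**Other dosing text.** Section 4.6 doses consolidation as "Vosaroxin intravenously on days 1 and 4 at a dose of 70 mg/m^2", again with the Phase I dose as an alternative. Section 4.7.4 lists 70 as level 0. Table 7 in 10.3 lists 90 as level 0 and 70 as the next step down.

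**Analysis text.** Section 10.2 counts six Phase I patients at the MTD among the 60 Phase II patients, but also gives a total of up to 84, as does 3.2. The efficacy and toxicity looks in 10.3 run every five patients with no reference to dose. Section 10.4 analyses everyone who had at least one dose, for efficacy as well as safety, with no split by starting dose.

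**The concern.** The two sets of instructions agree only if the MTD is 70. If it is 90, 4.4 sends Phase II to 90 while 4.5 also permits 70. If it is 50, the 'or' in 4.5, read literally, permits 70, a level that Phase I has just ruled out.

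The statistical consequence arises when 90 passes and Phase II is then given at 70. The six MTD patients in the 60, and any Phase II patients already treated at 90, then had a different induction dose. The primary ORR and the early futility looks would describe a mixture rather than the regimen carried forward. The same pooling applies to the toxicity looks in Table 10. Separately, if 90 fails and 70 passes, the 60 are all at 70, but the all-treated efficacy set in 10.4 still contains the failed cohort: 6 + 60 = 66.

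**Working it through.** **Inputs.** From 10.2: null ORR 0.40, target 0.60, exact binomial test, two-sided alpha 0.05 (0.025 in the upper tail), n = 60 with six from Phase I, stated power 82%. From Table 8, the upper stopping limits at 5, 10, …, 55 patients: 0, 2, 5, 7, 9, 12, 15, 17, 20, 22, 25. ORR by dose is not in the documents, so the values below are assumptions. Six is the only count at 90 that the documents support.

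**Step 1: the plan's own figures.** The critical value is the smallest r with P(X ≥ r | n = 60, 0.40) ≤ 0.025. P(X ≥ 32) = 0.02503 and P(X ≥ 33) = 0.0133, so r = 33. Power is P(X ≥ 33 | 0.60) = 0.822, which reproduces 82%. The Beta(1.2, 0.8) rule in 10.3 reproduces the Table 8 limits. An exact recursion through them gives a stopping probability of 0.8885 at ORR 0.40 (Table 9: 0.888) and 0.0815 at 0.60 (Table 9: 0.079). With these looks applied, power is 0.797.

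**Step 2: mixed doses.** Responders = Bin(6, p90) + Bin(54, p70). The expected pooled ORR is (6·p90 + 54·p70)/60 = p70 + 0.10·(p90 − p70).

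| ORR at 70 | ORR at 90 | Pooled ORR | P(≥33/60), no looks | With Table 8 looks, six first | Stopped by 10 patients |
|---|---|---|---|---|---|
| 0.60 | 0.60 | 0.600 | 0.822 | 0.797 | 0.019 |
| 0.60 | 0.55 | 0.595 | 0.801 | 0.765 | 0.032 |
| 0.60 | 0.50 | 0.590 | 0.778 | 0.729 | 0.051 |
| 0.60 | 0.40 | 0.580 | 0.729 | 0.641 | 0.114 |
| 0.40 | 0.40 | 0.400 | 0.013 | 0.012 | 0.192 |
| 0.40 | 0.45 | 0.405 | 0.016 | 0.015 | 0.140 |
| 0.40 | 0.50 | 0.410 | 0.020 | 0.019 | 0.099 |
| 0.40 | 0.60 | 0.420 | 0.028 | 0.027 | 0.043 |

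The false-positive chance passes 0.025 only for the 20-point gap. The early looks are more sensitive. If the six come first, the 5-patient look has nobody at 70 and the 10-patient look has four.

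**Step 3: does the overlap hold?** Section 3.2 adds 24 and 60 to reach 84. With six shared patients the maximum would be 24 + 54 = 78, so the total of 84 in 10.2 conflicts with the overlap stated in the same section. With no overlap, neither the 60 nor the Table 8 looks include the six, and Step 2 does not apply to them. Section 10.4 would still include them as 6 of 66.

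**Step 4: dropping unmatched patients.** For n = 54, P(X ≥ 29 | 0.40) = 0.0287 and P(X ≥ 30 | 0.40) = 0.0149, so reject at 30 or more. Power at 0.60 is 0.791, or 0.771 with the looks from 5 to 50.

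**The case against.** The best defence is that the intended dose is clear. Section 4.5 names 70 first and gives a reason, 4.6 uses 70, and 4.7.4 makes it level 0. That stands, so a reader who infers that the Phase II dose is simply unknown goes too far. What remains is that 3.2 and 4.4 still say otherwise, and the 'or' has no rule.

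A protocol also need not report whether 90 passed or whether the IND Office agreed, so the absence of those facts is not a fault. The cohort reports in 4.4, "including a separate cohort summary for each dose level tested", give that office a view by dose. They follow the Phase I toxicity assessment, however, and do not supply ORR by dose.

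A reader might infer that the step down from 90 is missing altogether, because 4.7.3 refers to 4.7.4 and that table starts at 70. In fact Table 7 and 4.4 item (b) both give 70 as the step below 90. The gap is only a missing row in the table to which 4.7.3 points.

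On size, the defence is largely right. Two points of ORR for a 20-point dose gap is small beside the exact 95% interval at 33/60, which runs from 41.6% to 67.9%. Section 4.5 expects equal efficacy, and then the bias is nil. Section 10.3 does not say that the six are counted first. Section 10.4 does plan tests of response against clinical characteristics, though it does not name dose.

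**Conclusion.** The conflict between 3.2 and 4.4 on one side and 4.5 on the other is certain from the text and should be fixed. The pooled-dose consequence holds only if 90 passed, Phase II then ran at 70, the six count in the 60, and ORR differs by dose. Under those conditions it is modest: 10% of the dose difference in the pooled ORR, and power of 0.765 or 0.729 instead of 0.797 for gaps of 5 or 10 points with the six first. Its direction is open. More patients at 90 would enlarge it, but no number is given. A reader might infer that the sample size is wrong or that the primary result is invalid. The documents support neither: 82% reproduces, and nothing shows that doses were in fact mixed. The inclusion of any failed Phase I cohort in the 10.4 efficacy set follows from the wording alone.

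**What to change.** 1. In 3.2, 4.4 and 4.5, state: 'Phase II vosaroxin dose is 70 mg/m² on days 1 and 4, or the Phase I MTD if that is lower.' Add the step from 90 to 70, already in Table 7, to 4.7.4.
2. In 10.2, state that Phase I patients count in the 60, and in the Table 8 and Table 10 looks, only if their induction dose is the Phase II dose. Reconcile the total of 84 with the overlap.
3. In 10.4, base the primary ORR on patients who start at the Phase II dose. Report ORR with 95% CI and first-cycle toxicity by starting dose, as description only.

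**Cost.** Amendment wording and one table. If the six match, nothing else changes. If they do not, there are two options. Either test 54, rejecting at 30 or more, and restate power as 0.791 (0.771 with the looks). Or treat 60 at the Phase II dose and keep 0.822 (0.797 with the looks). With one passing Phase I cohort the second option means 6 + 60 = 66 patients, six more than under the overlap reading and within the ceiling of 84. The estimate at 90 would be very imprecise: 3 of 6 has a 95% CI of 12% to 88%, so it cannot show equivalence.
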